### 7.2 Secondary endpoints

- Proportion of relapse-free patients at 24 and 48 months
- ARR at 24 months
- The time to sustained progression of disability from baseline up to 24 and 48 months
- Time to the first relapse from baseline up to 48 months
- Time to the second relapse from baseline up to 48 months

- Changes in mean number of T1 Gd+ lesions per MRI scan taken at 12, 24, 36 and 48 months compared to baseline
- Changes in mean number of active T2-weighted lesions per MRI scan taken at 12, 24, 36 and 48 months compared to baseline
- Changes in level of disability as measured by EDSS at 6, 12, 18, 24, 30, 36, 42 and 48 months compared to baseline
- No evidence of disease activity (NEDA-3) at 24 and 48 months
- The proportion of patients receiving rescue therapy according to local standards of care from baseline up to 48 months
- Patient adherence to Cladribine 10 mg tablets treatment after both dosing periods as assessed at 3 and 15 months (by counting used tablets from original packages as patients will be asked to bring them to the site).
- Frequency of adverse events interviewed or reported spontaneously by the patients or as noted on physical, MRI or laboratory examinations up to month 48
- Percentage of patients with at least 1 Common Terminology Criteria for Adverse Events (CTCAE) grade 3 or 4 Lymphocyte Toxicity up to month 48
- Median time to recovery from grade 3 or 4 Lymphocyte Toxicity
- Percentage of patients who developed herpes zoster infections or malignancies up to month 48

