**Assessment before therapy initiation (all answers have to be yes)**

- Lymphocyte count must be normal before initiating Cladribine 10 mg tablets in year 1
- MRI should be performed before initiating Cladribine 10 mg tablets (usually within 3 months) to exclude progressive multifocal leukoencephalopathy (PML)
- Patient weight
- Lymphocyte count
- Number of Cladribine 10 mg tablets to be used in the whole treatment course year 1

**V2 - Visit Month 3 Year 1** (2 months after the first dose of Cladribine 10 mg tablets in Year 1)

- Visit date
- Date of Cladribine 10 mg tablet therapy start
- Number of Cladribine 10 mg tablets really used in the whole treatment course year 1
- Lymphocyte count
- Any relapse and rescue therapy from the last visit
- Any AE from the last visit
- Concomitant medication (only corticosteroids, myorelaxants, analgesics, antidepressants, anxiolytics) from the last visit

**V3 - Visit Month 7 Year 1** (6 months after the first dose of Cladribine 10 mg tablets in Year 1)

- Visit date
- Lymphocyte count
- EDSS score
- Any relapse and rescue therapy from the last visit
- Any AE from the last visit
- Concomitant medication (only corticosteroids, myorelaxants, analgesics, antidepressants, anxiolytics) from the last visit

**V4 - Pre-dose Year 2** (12 months after the first dose of Cladribine 10 mg tablets in Year 1; For patients with lymphocyte count below 800 cells/mm^3 the treatment course in year 2 must be delayed for up to 6 months to allow for recovery of lymphocytes as per SmPC. For these patients V4 will be postponed until recovery - up to maximum of 6 months).

- Visit date
- Is patient eligible to continue Cladribine 10 mg tablets therapy as per SmPC? (yes/no)

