**Assessment before therapy initiation (all answers have to be yes)**

- Lymphocyte count must be at least 800 cells/mm^3 before initiating Cladribine 10 mg tablets in year 2
- MRI should be performed before continuing Cladribine 10 mg tablets to exclude PML (within 3 months)
- MRI status
- EDSS score
- Patient weight
- Lymphocyte count
- Number of Cladribine 10 mg tablets to be used in the whole treatment course year 2
- Any relapse and rescue therapy from the last visit
- Any AE from the last visit
- Concomitant medication (only corticosteroids, myorelaxants, analgesics, antidepressants, anxiolytics) from the last visit

**V5 - Visit Month 3 Year 2** (2 months after the first dose of Cladribine 10 mg tablets in Year 2)

- Visit date
- Date of Cladribine 10 mg tablet therapy start
- Number of Cladribine 10 mg tablets really used in the whole treatment course year 2
- Lymphocyte count
- Any relapse and rescue therapy from the last visit
- Any AE from the last visit
- Concomitant medication (only corticosteroids, myorelaxants, analgesics, antidepressants, anxiolytics) from the last visit

**V6 - Visit Month 7 Year 2** (6 months after the first dose of Cladribine 10 mg tablets in Year 2)

- Visit date
- Lymphocyte count
- EDSS score
- Any relapse and rescue therapy from the last visit
- Any AE from the last visit

- Concomitant medication (only corticosteroids, myorelaxants, analgesics, antidepressants, anxiolytics) from the last visit

**V7 - Visit Month 12 Year 2/Month 1 Year 3** (12 months after the first dose of Cladribine 10 mg tablets in Year 2)

- Visit date
- MRI status
- EDSS score
- Any relapse and rescue therapy from the last visit
- Any AE from the last visit
- Concomitant medication (only corticosteroids, myorelaxants, analgesics, antidepressants, anxiolytics) from the last visit

**V8 - Visit Month 7 Year 3** (18 months after the first dose of Cladribine 10 mg tablets in Year 2)

- Visit date
- EDSS score
- Any relapse and rescue therapy from the last visit
- Any AE from the last visit
- Concomitant medication (only corticosteroids, myorelaxants, analgesics, antidepressants, anxiolytics) from the last visit

**V9 - Visit Month 12 Year 3/Month 1 Year 4** (24 months after the first dose of Cladribine 10 mg tablets in Year 2)

- Visit date
- MRI status
- EDSS score
- Any relapse and rescue therapy from the last visit
- Any AE from the last visit

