- Concomitant medication (only corticosteroids, myorelaxants, analgesics, antidepressants, anxiolytics) from the last visit

**V10 - Visit Month 7 Year 4** (30 months after the first dose of Cladribine 10 mg tablets in Year 2)

- Visit date
- EDSS score
- Any relapse and rescue therapy from the last visit
- Any AE from the last visit
- Concomitant medication (only corticosteroids, myorelaxants, analgesics, antidepressants, anxiolytics) from the last visit

**EOS - Visit Month 12 Year 4** (36 months after the first dose of Cladribine 10 mg tablets in Year 2)/Premature Withdrawal Visit

- Visit date
- MRI status
- EDSS score
- Any relapse and rescue therapy from the last visit
- Any AE from the last visit

Concomitant medication (only corticosteroids, myorelaxants, analgesics, antidepressants, anxiolytics) from the last visit

Table 8-1: Flow chart

Year	Year 1			Year 2			Year 3		Year 4		
	pre-dose	3	7	pre-dose	3	7	1	7	1	7	12
Timing (month if applicable)	V1	V2	V3	V4	V5	V6	V7	V8	V9	V10	EOS /PW*
Informed consent	X										
Inclusion/Exclusion criteria	X										
Baseline characteristics (patient and disease)	X										
Patient weight	X			X							
Is patient eligible to start Cladribine 10 mg tablets therapy?	X			X							
MRI status	X			X			X		X		X
Lymphocyte count (or Blood count)	X	X	X	X	X	X					
Number of Cladribine 10 mg tablets to be used	X			X							
Date of Cladribine 10 mg tablet therapy start and number of Cladribine 10 mg tablets really used (as counted from original packages brought back to the site)		X			X						
EDSS	X		X	X		X	X	X	X	X	X
Any relapse and rescue therapy from the last visit		X	X	X	X	X	X	X	X	X	X
Any AE from the last visit		X	X	X	X	X	X	X	X	X	X
Concomitant medication (only corticosteroids, myorelaxants, analgesics, antidepressants, anxiolytics) from the last visit		X	X	X	X	X	X	X	X	X	X
Reasons for premature withdrawal, if applicable											X

\*PW – Premature Withdrawal Visit in case of patient premature withdrawal

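### Grade 3-4 lymphocyte toxicity is to be reported to month 48, but lymphocyte counts are collected only to V6 (about month 18), so later cases and recoveries rest on AE/AESI reports alone

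*Protocol*

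**What the plan says.** Section 7.2 lists two secondary endpoints that rest on a laboratory value: the percentage of patients with at least one CTCAE "grade 3 or 4 Lymphocyte Toxicity up to month 48", and "Median time to recovery from grade 3 or 4 Lymphocyte Toxicity". The first has a 48-month window. The second states neither a window nor an assessment schedule.

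The flow chart (Table 8-1) has a row "Lymphocyte count (or Blood count") that is marked at V1, V2, V3, V4, V5 and V6 and blank at V7, V8, V9, V10 and EOS. The visit lists in section 8.2 agree. V6 is placed "6 months after the first dose of Cladribine 10 mg tablets in Year 2" and EOS "36 months after the first dose of Cladribine 10 mg tablets in Year 2". For patients with a low count before the second course, section 8.2 says that "the treatment course in year 2 must be delayed for up to 6 months to allow for recovery of lymphocytes", and V4 itself is moved until the count has recovered.

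A second route of capture runs to the end of the study. Section 11 requires all AEs to be recorded from V1 to EOS/PW. Section 11.1 counts abnormal laboratory findings as AEs and names grade 3 and 4 lymphocyte toxicity as an AESI. Table 8-1 asks about AEs at every visit from V2 to EOS. Section 11.2.2 requires a detected AE to be followed until it resolves or is judged permanent.

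**The concern.** Both endpoints are defined by a measured count, yet the measurement stops well before the reporting window does. EDSS and MRI, which also support month-48 endpoints, keep their fields through to EOS; the lymphocyte count does not. If the percentage is published as a 48-month figure, readers will take it as the result of 48 months of comparable ascertainment. In fact one part would come from recorded values and the other from event reports, with no record of who was tested. Lymphocyte toxicity is one of only three AESIs in the study, so a reassuring late-period figure that partly reflects lack of testing would matter for the safety conclusions. The primary endpoint (ARR) is not affected.

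**Working it through.** **Inputs.** All come from section 8.2 and Table 8-1, in months from the first Year 1 dose. V2 = 2 and V3 = 6. V4 = 12 + d, where d is the delay of the second course (0 to 6). V5, V6 and EOS are 2, 6 and 36 months after the first Year 2 dose. I assume that this dose follows V4 directly.

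**Last count and end of study.**
- V6 = 12 + d + 6: month 18 for d = 0; month 24 for d = 6.
- EOS = 12 + d + 36: month 48 for d = 0; month 54 for d = 6.

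**Time without a count field.**
- d = 0: 48 − 18 = 30 months; 30/48 = 62.5%.
- d = 6, first 48 months: 48 − 24 = 24 months; 24/48 = 50%.
- d = 6, to EOS: 54 − 24 = 30 months; 30/54 = 56%.

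**Spacing of scheduled counts.**

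| Delay | Counts at month | Gaps (months) |
|---|---|---|
| 0 | 0, 2, 6, 12, 14, 18 | 2, 4, 6, 2, 4 |
| 6 | 0, 2, 6, 18, 20, 24 | 2, 4, 12, 2, 4 |

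On the visit data, recovery can thus be dated only to an interval of 2 to 6 months, or up to 12 months between V3 and a delayed V4. In the delayed patients V4 takes place once the count has recovered, so the low value that caused the delay has no visit field of its own.

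**What the AE/AESI route can supply after V6.**
1. It needs a blood count. Section 5.1 mandates no assessment, and the monitoring schedule in Table 3-1 is empty for Years 3 and 4.
2. It needs a grade. Up to V6 the CTCAE grade can be derived from the recorded value. After V6 it depends on the physician recognising grade 3 or 4 and reporting the AESI; the general AE severity scale in section 11.1 is mild, moderate or severe.
3. It leaves no trace of negative or absent tests, so the number of patients actually tested after V6 is unknown.
4. For a case open at V6, the recovery date comes from AE follow-up. Section 11.2.2 allows an event to be closed as permanent, for example if it continues at the end of the study, and no later count field is available to confirm resolution.

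**Size of the under-count.** It cannot be calculated. The protocol gives neither a rate of late grade 3-4 lymphopenia nor a frequency of routine testing in Years 3-4.

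**The case against.** The strongest reply is that the AE pathway is compulsory. Grade 3-4 lymphocyte toxicity is an AESI, section 11.2.2 requires prompt transmission to the marketing authorization holder, and detected events must be followed up. A reader might infer from the blank cells in Table 8-1 that late cases and recoveries are lost altogether. The protocol does not support that: a late case found on a routine test is reportable up to EOS, and a case open at V6 has a required route to an outcome. What does not follow is that ascertainment after V6 is complete, since reporting can only begin once somebody has tested.

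A reader might also infer that the median recovery time is biased short because unresolved cases drop out. The protocol names no estimator for this endpoint. Its statement in section 12.2 that missing data will not be replaced rules out imputation, not censoring, and the estimator may properly be left to the SAP. The direction is not clear in any case: leaving out unresolved cases would shorten the median, while dating recovery at the next sparse visit would lengthen it.

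Finally, the count schedule is deliberate. It mirrors the SmPC monitoring shown in Table 3-1, and a non-interventional study cannot add blood tests. That stands, and it is a good reason not to require new tests. It does not justify a 48-month label on a count-based percentage, and section 8.1 already accepts chart data as a source. Section 5.1 does say that all described assessments will be collected, but no lymphocyte count is described after V6.

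**Conclusion.** The mismatch is real and should be corrected. Count-based ascertainment ends at about month 18 (up to about month 24 with a delayed second course), against a stated window of 48 months. Between 24 and 30 of those 48 months depend on AE/AESI reports alone. Incidence to month 48 may therefore be under-ascertained, and recovery times are known only to wide intervals. The 50% to 62.5% is a share of calendar time without a count field; it should not be read as a share of events missed. The conclusion rests on the visit timing in section 8.2 and on the second course starting at V4. It does not depend on any assumption about how the SAP will estimate the median. These are descriptive secondary safety endpoints, so the point is worth fixing but does not threaten the study's main result.

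**What to change.** Add to the eCRF, at every visit from V2 to EOS, a repeating field for the date and value of any lymphocyte count since the last visit. It would be filled from routine results already in the chart, with no added blood test. Starting at V2 also picks up counts taken between V3 and a delayed V4. Report how many patients had any count after V6, so that the 48-month percentage can be read against the number tested.

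If the field is not added, restrict the count-based percentage to V1-V6 and present later cases separately, labelled as AE/AESI-reported. That keeps the late AESI cases, which the protocol requires to be collected up to EOS.

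The cost is one repeating field and more data entry for sites. The yield is uncertain: section 5.1 says that patients usually attend every 3 months, but not whether blood counts are then taken, and few may exist in Years 3-4. Even so, the number tested would be known.

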## 8 DATA COLLECTION

### 8.1 Data source

Patients' medical charts, any relevant diagnostic reports including description of MRI scans recorded as part of the standard of care and number of actually used Cladribine 10 mg tablets for adherence evaluation as described in section 5.1 are the source documents for study data collection. Clinical information recorded in patients' medical charts and/or diagnostic reports will be entered into the eCRF (Electronic case report form).

### 8.2 Collected Data

#### V1 - Pre-dose Year 1 Visit

Date of visit, date of ICF signature (if different), meeting of eligibility criteria (yes/no)

Basic demographic data:

- Year of birth
- Gender

Baseline characteristics:

- Relevant medical history
- Relevant concurrent diseases/concomitant medications

Condition of MS:

- Date of MS diagnosis
- Medical history related to MS
- Previous MS therapy
- Number of relapses in the last 12 months
- Current EDSS score
- Current MRI status (within 3 months)

#### Pre-treatment requirements

- Is patient eligible to start Cladribine 10 mg tablets therapy as per SmPC? (yes/no)

**Contraindications (all answers have to be no):**

- Hypersensitivity to the active substance or to any of the excipients (yes/no)
- Infection with human immunodeficiency virus (HIV) (yes/no)
- Active chronic infection (tuberculosis or hepatitis) (yes/no)
- Initiation of cladribine treatment in immunocompromised patients, including patients currently receiving immunosuppressive or myelosuppressive therapy (yes/no)
- Active malignancy (yes/no)
- Moderate or severe renal impairment (creatinine clearance <60 mL/min) (yes/no)
- Pregnancy and breast-feeding (yes/no)

**Recommended screening for infections (all answers have to be yes)** - A delay in initiation of Cladribine 10 mg tablets should also be considered in patients with an acute infection until the infection is fully controlled.

- Active or latent tuberculosis excluded (yes/no)
- Active infection with hepatitis B virus (HBV) excluded (yes/no)
- Active infection with hepatitis C (HCV) excluded (yes/no)

**Vaccination – If vaccination is needed, initiation of treatment with Cladribine 10 mg tablets must be postponed for 4 to 6 weeks to allow for the full effect of vaccination to occur**

- Vaccination of patients who are varicella zoster virus antibody-negative within 4–6 weeks before initiation of Cladribine 10 mg tablets (yes/no)
- Vaccination with live or attenuated live vaccines within 4–6 weeks before initiation of Cladribine 10 mg tablets (yes/no)

**Pregnancy and contraception (all answers have to be yes)**

- Pregnancy excluded in women of childbearing potential (yes/no)
- Women of childbearing potential must agree to prevent pregnancy by use of effective contraception during Cladribine 10 mg tablets treatment and for at least 6 months after the last dose. Women using systemically acting hormonal contraceptives should add a barrier method during Cladribine 10 mg tablets treatment and for at least 4 weeks after the last dose in each treatment year. Women who become pregnant under therapy with Cladribine 10 mg tablets should discontinue treatment. (yes/no)
- Male patients must agree to take precautions to prevent pregnancy of their partner during Cladribine 10 mg tablets treatment and for at least 6 months after the last dose. (yes/no)

**Assessment before therapy initiation (all answers have to be yes)**

- Lymphocyte count must be normal before initiating Cladribine 10 mg tablets in year 1
- MRI should be performed before initiating Cladribine 10 mg tablets (usually within 3 months) to exclude progressive multifocal leukoencephalopathy (PML)
- Patient weight
- Lymphocyte count
- Number of Cladribine 10 mg tablets to be used in the whole treatment course year 1

**V2 - Visit Month 3 Year 1** (2 months after the first dose of Cladribine 10 mg tablets in Year 1)

- Visit date
- Date of Cladribine 10 mg tablet therapy start
- Number of Cladribine 10 mg tablets really used in the whole treatment course year 1
- Lymphocyte count
- Any relapse and rescue therapy from the last visit
- Any AE from the last visit
- Concomitant medication (only corticosteroids, myorelaxants, analgesics, antidepressants, anxiolytics) from the last visit

**V3 - Visit Month 7 Year 1** (6 months after the first dose of Cladribine 10 mg tablets in Year 1)

- Visit date
- Lymphocyte count
- EDSS score
- Any relapse and rescue therapy from the last visit
- Any AE from the last visit
- Concomitant medication (only corticosteroids, myorelaxants, analgesics, antidepressants, anxiolytics) from the last visit

**V4 - Pre-dose Year 2** (12 months after the first dose of Cladribine 10 mg tablets in Year 1; For patients with lymphocyte count below 800 cells/mm^3 the treatment course in year 2 must be delayed for up to 6 months to allow for recovery of lymphocytes as per SmPC. For these patients V4 will be postponed until recovery - up to maximum of 6 months).

- Visit date
- Is patient eligible to continue Cladribine 10 mg tablets therapy as per SmPC? (yes/no)

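### V4 moves to the date of lymphocyte recovery, so in patients who recover within the limit the count that caused the Year-2 delay has no scheduled entry

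*Protocol*

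**What the plan says.** Protocol section 8.2 sets V3 at "6 months after the first dose of Cladribine 10 mg tablets in Year 1" and V4 at 12 months after that dose. When the count is below 800 cells/mm3, "the treatment course in year 2 must be delayed for up to 6 months to allow for recovery of lymphocytes as per SmPC". The next sentence applies the delay to the visit as well as the dosing: "For these patients V4 will be postponed until recovery - up to maximum of 6 months". (The parallel sentence in the Protocol Summary has lost its subject; section 8.2 is the place that names V4.)

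The V4 list contains one lymphocyte count entry. It also contains an eligibility check, "Lymphocyte count must be at least 800 cells/mm"3 "before initiating Cladribine 10 mg tablets in year 2", and a yes/no item on whether the patient may continue treatment. Table 8-1 schedules lymphocyte counts at V1 to V6 and has no visit between V3 and V4.

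Two secondary endpoints in section 7.2 rest on lymphocyte data: the percentage of patients with at least one grade 3 or 4 lymphocyte toxicity up to month 48, and "Median time to recovery from grade 3 or 4 Lymphocyte Toxicity". Section 12.2 describes all continuous variables with summary statistics and does not replace missing data.

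**The concern.** Whether the month-12 count becomes a scheduled data point depends on its own value. A patient at or above 800 has V4 on time and the count is entered. A patient below 800 has V4 moved, and if the count recovers within the limit, the later, higher value fills the only V4 entry. The counts left out of the schedule are the low ones.

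Two things are at stake. Any by-visit description of Year-2 pre-dose counts will look better than the month-12 counts did. And in the stretch of follow-up where lymphopenia decides management, the schedule contributes nothing to the grade 3-4 percentage or to time to recovery, so both depend on what sites report as adverse events. An analysis plan cannot repair this later, because sections 8.2 and Table 8-1 determine what is entered.

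**Working it through.** The protocol states no figure to reproduce. The check is visit timing plus a sorting of patients by what V4 can show.

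**Inputs (section 8.2, months after the first Year-1 dose):** V3 at month 6; V4 at month 12; maximum postponement 6 months; threshold 800 cells/mm3.

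**Interval between scheduled counts.** With a postponement of d months, 0 ≤ d ≤ 6:

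- gap = (12 + d) − 6 = 6 + d
- no delay: 6 + 0 = 6 months
- longest delay: 6 + 6 = 12 months, with V4 at month 18

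The triggering count, at about month 12, falls inside that gap.

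**What the single V4 count can show:**

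| Patient at about month 12 | When V4 happens | V4 count |
|---|---|---|
| (a) 800 or above | about month 12 | the month-12 value |
| (b) below 800, recovers within 6 months | at recovery, up to month 18 | the recovered value |
| (c) below 800, not recovered at the limit | about month 18 | can be low, with eligibility answered no |

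Only in group (b) is a low value replaced by a recovered one. In (a) nothing is lost. In (c) the low state is still visible at V4. Because (b) exchanges low values for higher ones and no group does the reverse by rule, the V4 distribution is shifted upward relative to month 12.

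**Effect on the two endpoints, using scheduled counts alone.** If a grade 3-4 count is seen at V3, recovery can be placed only between month 6 and V4, an interval that widens from 6 months to as much as 12. If a grade 3-4 episode begins after V3 and resolves before a postponed V4, the schedule shows nothing. In both cases the missing information has to come from the adverse event record.

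**Size.** The bias depends on the share of patients in group (b) and on how far their counts rise. The protocol gives neither, so no figure can be derived.

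**The case against.** The strongest reply is that the counts can reach the database by other routes. Section 5.1 calls the schedule approximate and says the described assessments are collected and then assigned to windows. Section 11 requires all adverse events to be recorded from V1 to the end of study, whatever their severity. Section 11.1 counts an abnormal laboratory finding as a possible adverse event and makes grade 3-4 lymphocyte toxicity an event of special interest. Section 11.2.2 requires follow-up to resolution. Sections 9.1 and 9.3 leave eCRF instructions and data procedures to other documents, so a repeatable laboratory field may exist.

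Much of this stands. Reported grade 3-4 events should be captured with a course and an outcome, and no endpoint is defined on the V4 count alone. It does not close the gap. For a delayed patient the described V4 assessment is the postponed one, and nothing says that the month-12 count is entered as well, or which of two counts would be V4. No rule makes a count below 800 reportable in itself. The protocol gives no CTCAE cut-offs, so it does not show which such counts are grade 3-4. Following an event to resolution does not require dated serial counts.

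The other side is also right on the reason for delay. Only low lymphocytes postpone V4 itself, V4 is dated, and the Year-2 start date is recorded separately at V5. A late V4 therefore largely marks a lymphopenia delay, while a delay for infection or vaccination would tend to show as an on-time V4 with a late start. A reason field would confirm this inference, but it is not the only means of telling delays apart.

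**Conclusion.** The point holds for patients below 800 cells/mm3 at about month 12 who recover within the 6-month limit. Their single V4 count is the recovered value, the triggering count and any repeats have no scheduled entry, and the gap between scheduled counts can reach 12 months instead of 6. Scheduled Year-2 pre-dose counts are selected upward, and for this interval the two grade 3-4 endpoints rest on adverse event reporting.

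Three stronger readings are not supported:

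- A reader might infer that Year-2 pre-dose counts show only recovered patients, or that a low count can never appear at V4. The 6-month limit and the yes/no eligibility item allow a low V4 count, the 800 threshold is a condition for dosing and not for holding the visit, and patients never below 800 also contribute.
- A reader might infer that the triggering counts are lost to the study. They lack a scheduled entry; some may arrive through event reporting.
- A reader might set a zero share below 800 at V4 against an assumed month-12 share such as 10% to 20%. The protocol gives no delay rate. The zero is true by construction among patients who start the second course, and the other figure uses a different denominator.

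The conclusion assumes that the data collected are those listed in section 8.2 and Table 8-1. It is worth correcting because the selection follows from a stated rule and the remedy is cheap.

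**What to change.** In section 8.2 and Table 8-1:

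- Keep a month-12 lymphocyte entry, with value and date, for every patient who has a standard-of-care count at that time, including the count that led to a delay.
- Add dated repeat entries for counts available in the chart up to the Year-2 start.
- Record the reason for any delay of the second course.
- State that these counts are used together with the event-of-special-interest data for the grade 3-4 percentage and for time to recovery.

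The charts are already the data source (section 8.1), and the decision to delay rests on these counts, so no new test is needed. The cost is a repeatable eCRF field and a small amount of extra data entry for delayed patients. No change to the dosing or delay rule is proposed.
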